Section 1.1 Synopsis: Key Objectives and Endpoints	HBe antibody (anti-HBeAg) levels have been re-classified as a categorical variable (previously a continuous variable)	This corrects an error in the original protocol.
	The analysis method for the time to maximum ALT has been updated from Kaplan-Meier to Turnbull	As visit spacing gets longer over time, interval censored method is more appropriate.
Section 1.3: Schedule of Activities	The Day 11 visit window was been updated from ± 3 days to ± 1 day	Updated to avoid potential overlap of the Day 8 and Day 11 visits
	Collection of PBMC samples for immunophenotyping updated from "Baseline, Day 8 (Week 2), Day 15 (Week 3), Day 29 (Week 5), Day 85 (Week 13), Day 162 (Week 24), Day 246 (Week 36) and Early Withdrawal" to "Baseline, Day 29 (Week 5), Day 246 (Week 36) and Early Withdrawal."	Amended to reduce sampling timepoints due to increased blood volume required for PBMC analysis.

Section # and Name	Description of Change	Brief Rationale
	The description of the standard examination has been updated from brief physical exam to symptoms directed exam	Updated to reflect risk reduction practices in limiting physical contact due to COVID-19 and to align with assessments covered by home nursing licenses.
	Clarification has been added that PK sample should be collected pre-dose.	This corrects an error in the original protocol.
	Guidance has been added that a fine needle aspiration (FNA) sample not to be collected if the participant has already withdrawn from treatment	Updated to reduce burden on participants who no longer wish to continue study treatment.
	A urine or serum pregnancy test has been added as an optional assessment at Day 1	Added for instances where the Screening serum human chorionic gonadotrophin (hCG) pregnancy test was >24 hours pre-dose first dose.
	The Week 28, 32 and 36 day numbers have been updated to Day 190, 218 and 246, respectively.	This corrects an error in the original protocol.
	The collection of samples for genetic resource have been removed from the SoA at all timepoints other than Week -1 (Baseline)	This corrects an error in the original protocol.
Section 2.3.1: Risk Assessment	Additional text added on risk with COVID-19 infection	Provide description of risk of COVID-19 infection in hepatitis B population
Section 2.3.3 Overall Benefit: Risk Conclusion	Additional text added on benefit/risk with COVID-19 infection	Include COVID-19 risk in the overall benefit:risk assessment
Section 3: Objectives and Endpoints	HBe antibody (anti-HBeAg) levels have been re-classified as a categorical variable (previously a continuous variable)	This corrects an error in the original protocol.
	The analysis method for the time to maximum ALT has been updated from Kaplan-Meier to Turnbull	As visit spacing gets longer over time, interval censored method is more appropriate. Turnbull method chosen, and this is consistent with Study 209348 (B-Together).
	Immunophenotyping added to list of possible measures for markers of immune cell function	To further expand the list of potential measures which may be used in the investigation of immune cell function.
Section 5.2 Exclusion Criteria	Exclusion criteria 8 and 9 have been re-written	Re-written following a request for clarification following protocol review by the MHRA.
Section 6.3: Measures to Minimize Bias: Randomization and Blinding	Additional text added on bias mitigation	Updated to include reference to the blinding plan
Section 6.8.2 Prohibited Medications and Non-Drug Therapies	Included anti-coagulation therapies as prohibited medication and non-drug therapies	To be consistent with exclusion criteria

Section # and Name	Description of Change	Brief Rationale
Section 7.1.1: Liver Chemistry Monitoring and Stopping Criteria	
Additional text added in 'Bold'
 
 • Any clinically significant deterioration from the baseline in the liver parameters must be confirmed by retesting ALT, total bilirubin, direct bilirubin, and INR (if available). • Cases such as Gilbert syndrome, where baseline bilirubin values are high, should be discussed with the medical monitor, to assess if it is a case of drug-induced liver injury (DILI) or the participant may continue with dosing. 	To clarify and identify instances where advice from the medical monitor should be sought
Section 7.1.3: Haematological Stopping Criteria	Additional text added around haematological stopping criteria	Updated to provide additional clarity.
Section 7.1.5: Study Intervention Restart or Rechallenge after Stopping Criteria Met	Added text in 'Bold' as follows: Institutional Review Boards (IRB)/Independent Ethics Committees (IEC) approval of study intervention restart has been obtained (if required) .	This corrects an error in the original protocol.
Section 8.2.1: Physical Examinations	Description of post-baseline brief physical examination updated to symptoms directed examination	Updated to reflect risk reduction practices in limiting physical contact due to COVID-19 and to align with assessments covered by home nursing licenses.
Section 8.2.3: Vital Signs	Requirement for vital sign measurement in a semi-supine position removed.	Updated as not required.
Section 9.4.4: Secondary Endpoint(s)	HBe antibody (anti-HBeAg) changed from a continuous to a categorical variable	This is to represent the data which have received since the start of the study.
	The analysis method for the time to maximum ALT has been updated from Kaplan-Meier to Turnbull	As visit spacing gets longer over time, interval censored method is more appropriate.
Section 9.6: Independent Data Monitoring Committee (IDMC)	Additional detail added regarding the timing of IDMC safety reviews	Updated to describe the planned safety reviews
Section 10.2: Appendix 2 Clinical Laboratory Tests	Additional text regarding processing of PBMC samples	Updated to allow for local laboratory processing of PBMC samples.
	Bilirubin SAE reporting requirements updated from $\leq 2 \times \text{ULN}$ to $\geq 2 \times \text{ULN}$	To correct an error in the definition.
Section 10.6: Appendix 6: Liver Safety: Required Actions and Follow-up Assessments and Study Intervention Restart Guidelines	Added text in 'Bold' as follows: Institutional Review Boards (IRB)/Independent Ethics Committees (IEC) approval of study intervention restart has been obtained (if required) .	This corrects an error in the original protocol.

TABLE OF CONTENTS

	PAGE
PROTOCOL AMENDMENT SUMMARY OF CHANGES TABLE.....	3
1. PROTOCOL SUMMARY	9
1.1. Synopsis	9
1.2. Schema	13
1.3. Schedule of Activities (SoA).....	13
2. INTRODUCTION.....	19
2.1. Study Rationale	19
2.2. Background	19
2.3. Benefit/Risk Assessment	21
2.3.1. Risk Assessment	21
2.3.2. Benefit Assessment	24
2.3.3. Overall Benefit: Risk Conclusion	24
3. OBJECTIVES AND ENDPOINTS.....	25
4. STUDY DESIGN	28
4.1. Overall Design	28
4.2. Scientific Rationale for Study Design	28
4.2.1. Participant Input into Design	32
4.3. Justification for Dose	32
4.4. End of Study Definition	34
5. STUDY POPULATION	34
5.1. Inclusion Criteria	35
5.2. Exclusion Criteria.....	36
5.3. Lifestyle Considerations.....	39
5.3.1. Alcohol and Tobacco	39
5.3.2. Activity	39
5.4. Screen Failures.....	39

1. PROTOCOL SUMMARY

1.1. Synopsis

Title:

B-Fine: An open label, single arm study to mechanistically interrogate the therapeutic effect of GSK3228836 in patients with Chronic Hepatitis B via intrahepatic immunophenotyping

Rationale:

B-Fine is an exploratory study of the therapeutic mechanism of GSK3228836 in participants with chronic hepatitis B (CHB) on stable nucleos(t)ide therapy. The study will investigate the virologic and immunologic correlates of HBsAg loss observed in participants when treated for 12 weeks with 300 mg GSK3228836. Repeat fine needle aspirates of the liver will be performed to enable analysis of liver-resident immune cells to investigate any immunomodulatory properties of GSK3228836 and to study the biology of underlying treatment-associated liver flares. Longitudinal analyses of blood-borne inflammatory signatures and virological assessments of CHB infection will be performed in parallel.

Key Objectives and Endpoints:

Objectives	Estimands/Endpoints
Primary	
Efficacy: To assess the effect of 12 weeks of GSK3228836 on serum hepatitis B virus surface antigen (HBsAg) levels in participants with CHB	
The Primary Estimand supporting the primary objective of the study is defined as:
 
 Population: Participants with CHB who receive at least one dose of investigational product (IP) Treatment: 300 mg GSK3228836 for 12 weeks (also on stable nucleos(t)ide therapy) Variable: Achieving serum HBsAg level <lower limit of quantitation (LLOQ) at any time point up to and including Week 12 without the use of pegylated (PEG)-interferon or other immunomodulator therapies Population-level summary: Percent of participants that achieve serum HBsAg level <LLOQ Intercurrent events: Discontinuation of, interruption of, and adherence to IP will be ignored (treatment policy). 
The primary estimand is the percentage of participants with CHB receiving 300 mg GSK3228836 for 12 weeks (with at least one dose of IP) who achieve serum HBsAg level <LLOQ at any time point up to and including Week 12 without the use of PEG-interferon or other immunomodulator therapies, regardless of completing IP, interruptions in IP or adherence to IP.

Objectives	Estimands/Endpoints
Secondary 
Efficacy: To assess sustainability of serum HBsAg loss by GSK3228836 for up to 24 weeks off-treatment.
	
The Estimand supporting the objective is defined as:
 
 Population: Participants with CHB who receive at least one dose of IP Treatment: 300 mg GSK3228836 for 12 weeks (also on stable nucleos(t)ide therapy) Variables: 
 Sustained HBsAg Response (HBsAg <LLOQ) for 24 weeks after the planned end of GSK3228836 treatment 
 HBsAg from Week 13 to Week 36 will be used to assess sustained HBsAg response after the planned end of GSK3228836 treatment without the use of PEG-interferon or other immunomodulator therapies. Sustained HBsAg Response (HBsAg <LLOQ) for 24 weeks after the actual end of GSK3228836 treatment 
 HBsAg for 24 weeks after end of actual treatment will also be used to assess sustained HBsAg response after the actual end of GSK3228836 treatment without the use of PEG-interferon or other immunomodulator therapies. Intercurrent events: Discontinuation of, interruption of, and adherence to IP will be ignored (treatment policy). 
The group of estimands supporting this objective in participants with CHB receiving 300 mg GSK3228836 for 12 weeks (with at least one dose of IP) is the percentage of participants for each variable regardless of completing IP, interruptions in IP or adherence to IP, without the use of PEG-interferon or other immunomodulator therapies.


Efficacy: To assess sustainability of serum HBsAg and HBV DNA loss by GSK3228836 for up to 24 weeks off treatment.
	
The Estimand supporting the objective is defined as:
 
 Population: Participants with CHB who receive at least one dose of IP Treatment: 300 mg GSK3228836 for 12 weeks (also on stable nucleos(t)ide therapy) Variables: 
 Sustained Virologic Response (HBsAg <LLOQ and HBV DNA <LLOQ) for 24 weeks after the planned end of GSK3228836 treatment without the use of PEG-interferon or other immunomodulator therapies. 
 HBsAg and HBV DNA from Week 13 to Week 36 will be used to assess sustained virologic response after the planned end of GSK3228836 treatment. Sustained Virologic Response (HBsAg <LLOQ and HBV DNA <LLOQ) for 24 weeks after the actual end of GSK3228836 treatment without the use of PEG-interferon or other immunomodulator therapies 
 HBsAg and HBV DNA for 24 weeks after end of actual treatment will be used to assess sustained virologic response after the actual end of GSK3228836 treatment. Intercurrent events: Discontinuation of, interruption of, and adherence to IP will be ignored (treatment policy). 
The group of estimands supporting this objective in participants with CHB receiving 300 mg GSK3228836 for 12 weeks (with at least one dose of IP) is the percentage of participants for each variable regardless of completing IP, interruptions in IP or adherence to IP, without the use of PEG-interferon or other immunomodulator therapies.

Objectives	Estimands/Endpoints

Efficacy: To assess the effect of 12 weeks GSK3228836 on biomarkers and virus-specific antibody responses
	
Estimands supporting the secondary objective of assessing the effect of 12 weeks GSK3228836 on biomarkers and virus-specific antibody responses are defined as follows:
 
 Population: Participants with CHB who receive at least one dose of IP Treatment: 300 mg GSK3228836 for 12 weeks (also on stable nucleos(t)ide therapy) Intercurrent events: Discontinuation of, interruption of, adherence to IP will be ignored (treatment policy). PEG-interferon or other immunomodulator therapies will be handled with hypothetical strategy. 
1) Categorical Variables:
 
 Achieving: 
 HBsAg <LLOQ over time HBV DNA <LLOQ over time HBsAg and HBV DNA <LLOQ over time Categorical changes from baseline in HBsAg (e.g. <0.5, ≥0.5, ≥1, ≥1.5, ≥3 \log_{10} IU/mL) over time. ALT>3X ULN at over time HBe antibody (anti-HBeAg) levels over time 
Population summary: percentage of participants in each category.
 
2) Continuous Variables:
 
 Actual values and change from baseline over time for HBsAg and HBV DNA HBs antibody (anti-HBsAg) levels over time Area under the curve (AUC) for ALT on treatment (12 weeks), during follow up (24 weeks), and on treatment + follow up (36 weeks). 
Population summary: mean values and/or mean changes from baseline for each variable
 
3) Time to Event Variable
 
 Time to Maximum ALT (ALT must be greater than 3xULN) during 36 weeks of treatment + follow up 
Population summary: Turnbull estimate for median Time to Maximum ALT (>3xULN)
 
The group of estimands supporting this objective in participants with CHB receiving 300 mg GSK3228836 for 12 weeks (with at least one dose of IP) are the population summary for each variable in the absence of PEG-interferon or other immunomodulator therapies, regardless of completing IP, interruptions in IP, or adherence to IP.

Overall Design:

This study is a Phase IIa, multi-centre open label exploratory study of the therapeutic mechanism of GSK3228836 in participants with HBeAg-negative CHB on stable nucleos(t)ide therapy using repeat fine needle aspirations of the liver for intrahepatic immunophenotyping.

The study consists of a single treatment arm

- 300 mg GSK3228836 for 12 weeks (loading schedule on Day 4 and Day 11). Participants will continue to receive their stable nucleos(t)ide therapy.

After the 12 weeks of dosing with GSK3228836, there will be a post-treatment follow-up period of 24 weeks.

Brief Summary:

The purpose of this study is to determine the therapeutic mechanism of GSK3228836 in participants with CHB. Study details include:

Study Duration: 37 weeks (45 weeks if include screening and flexible visit windows)

Treatment Duration: 12 weeks

Visit Frequency: Twice a week for the first 2 weeks, once a week through Week 14, once at Week 16, and once every 4 weeks thereafter

Study Hypothesis: GSK3228836 treatment will result in phenotypic changes in intrahepatic immunity associated with loss of HBsAg and treatment-emergent changes in ALT

Health Measurement/Observation: HBsAg <LLOQ

Number of Participants:

The study will enrol approximately 20 participants, but no more than 24.

Note: "Enrolled" means a participant's, or their legally acceptable representative's, agreement to participate in a clinical study following completion of the informed consent and eligibility process. Potential participants who are screened for the purpose of determining eligibility for the study, but do not participate in the study, are not considered enrolled, unless otherwise specified by the protocol.

Intervention Groups and Duration:

[figure not shown]
The total duration of the study, including screening, treatment and post-treatment follow-up, is not expected to exceed 45 weeks.

- 45-day screening window. Eligible participants who fall out of the 45-day window may be re-screened at the discretion of the Investigator/site
- Up to 1 week of pre-treatment assessments (including baseline FNA)
- 12 weeks treatment with GSK3228836
- 24 weeks post treatment follow-up (+ up to 10 days)

There are no plans for dose adjustments. Individual dose adjustments for safety are outlined in the monitoring/stopping criteria.

Data Monitoring/ Other Committee: Yes

1.2. Schema

An optional 6th FNA may be included between Weeks 6 and 36 following discussion between investigator and medical monitor.

1.3. Schedule of Activities (SoA)

In selected countries/sites, participants will have the option to use a centralised home nursing provider. Only selected visits will have the option to be performed as a home visit. Home visits may include drug administration, blood draws, participant assessments and data collection. The full specifications of the home nursing services will be outlined in the study reference manual (SRM).

Table 1 Screening

ASSESSMENTS (45 Day window)	
Informed Consent	X
Inclusion and exclusion criteria	X
Demography	X
Medical history (includes substance usage) and current medical conditions	X
Medication history and concomitant medication review	X
Full physical exam including height and weight	X
Vital signs	X
12-lead ECG	X
LABORATORY ASSESSMENTS	
Serum hCG pregnancy test (women of child-bearing potential)	X
FSH/Estradiol (to confirm status of women of non-child-bearing potential) ¹	X
Hematology/Chemistry/Urinalysis	X
Urine ACR	X
PT, INR, aPTT	X
HIV, hepatitis D, and hepatitis C screen	X
Hepatitis B profile (HBsAg, HBV DNA, HBeAg)	X
Alpha-fetoprotein	X
APRI/Fibrosure/Fibrotest	X
ANCA ²	X
Complement C3, C4, C5a, hsCRP, MCP-1, complement Bb, Ang-II	X

1. As appropriate to confirm menopause.
2. With MPO-ANCA, PR3-ANCA if results are positive or border-line positive

Table 2 On-Treatment Day -7 to Day 50

Assessments	Day -7 to Day -1	D1	D4	D8	D11	D15	D22	D29	D36	D43	D50
	Week-1 (Baseline)	W1	W1	W2	W2	W3	W4	W5	W6	W7	W8
Window		±1 day				± 3 days					
Study treatment dosing ¹		X	X	X	X	X	X	X	X	X	X
Safety Assessments											
AE/SAE review	X	X	X	X	X	X	X	X	X	X	X
Concomitant medication review	X	X	X	X	X	X	X	X	X	X	X
Symptoms directed exam	X	X						X			
Vital signs	X	X	X	X	X	X	X	X	X	X	X
Injection site reactions		X	X	X	X	X	X	X	X	X	X
Laboratory											
Pregnancy test (women of child bearing potential) ²	X							X			
Hematology ³ [includes platelet count and WBC]	X	X		X		X	X	X	X	X	X
PT, INR, aPTT	X	X				X		X			
Chemistry	X	X		X		X	X	X	X	X	X
Urinalysis	X	X		X		X	X	X	X	X	X
Urine ACR	X	X				X		X			X
HBsAg and HBV DNA	X	X		X		X	X	X	X	X	X
Anti-HBsAg	X							X			
Anti-HBeAg	X							X			
HBV RNA, HBcrAg, and sequencing (HBV genotype/phenotype, HBV DNA and/or RNA)	X					X	X	X			X
Complement C3, Complement C4, hs-CRP, MCP-1	X	X				X		X			X
Complement C5a, Complement factor Bb	X	X				X		X			X
ANCA, Ang II	X	X						X			
PK ⁴			X	X		X	X	X	X	X	X
Fine needle aspiration of liver ⁵	X					X ⁶		X ⁶			
PBMC Collection for immunophenotyping	X							X			
Soluble Protein	X			X		X	X	X			X
PAXGene RNA for expression analysis in whole blood	X			X		X		X			
Genetics	X										
Archived samples [serum; plasma]	X			X		X		X		X	

Assessments	Day -7 to Day -1	D1	D4	D8	D11	D15	D22	D29	D36	D43	D50
	Week-1 (Baseline)	W1	W1	W2	W2	W3	W4	W5	W6	W7	W8
Optional Assessments											
Urine or serum pregnancy test ⁷		X									
Optional: fine needle aspiration of liver ⁸									X	X	X
Optional: PBMC Collection for immunophenotyping ⁹									X	X	X
Optional: Soluble Protein ⁹									X	X	X
Optional: PAXGene RNA for expression analysis in whole blood ⁹									X	X	X

1. Dosing to occur only after the completion of all assessments to determine dosing is safe to proceed
2. Women of childbearing potential (WOCBP) must have both:
 - a. A confirmed menstrual period prior to the first dose of study intervention; additional evaluation (e.g., amenorrhea in athletes, birth control) should also be considered
 - b. AND a negative highly sensitive pregnancy test [urine or serum] before the first dose of study treatment
3. Hematology- platelet count to be analyzed at local laboratory prior to dose; hematology samples to be collected for central laboratory assessments in parallel
4. PK samples are to be taken pre-dose
5. FNA will only be collected if the investigator deems it appropriate
6. Within 3 hours after study treatment dosing in Week 3 and Week 5. Sample not to be collected if the participant has already withdrawn from treatment.
7. Only to be conducted for women of child-bearing potential if the Screening serum hCG pregnancy test was >24 hours pre-dose first dose.
8. An optional additional FNA may be collected anytime between Week 6 and Week 36 following discussion between investigator and medical monitor based on unexpected changes in HBsAg or ALT. Only 1 additional FNA may be collected for each participant.
9. Only to be collected if the optional FNA is collected at this visit and has not already been collected as part of the standard assessments.

Table 3 On-Treatment Day 57 to Day 78

Assessments	D57 W9	D64 W10	D71 W11	D78 W12
Window		\pm 3 days		
Study treatment dosing	X	X	X	X
Safety Assessments				
AE/SAE review	X	X	X	X
Concomitant medication review	X	X	X	X
Symptoms directed exam	X			
Vital signs	X	X	X	X
Injection site reactions	X	X	X	X
Laboratory				
Pregnancy test (women of child bearing potential)	X			
Hematology ¹ [includes platelet count and WBC with differential]	X	X	X	X
PT, INR, aPTT	X			
Chemistry	X	X	X	X
Urinalysis	X	X	X	X
Urine ACR	X		X	
HBsAg and HBV DNA	X	X	X	X
Anti-HBsAg	X			
Anti-HBeAg	X			
HBV RNA, HBcrAg, and Sequencing (HBV genotype/phenotype; HBV DNA and/or RNA)				X
Complement C3, Complement C4, hs-CRP, MCP-1	X		X	
Complement C5a, Complement factor Bb	X		X	
ANCA, Ang II	X			
PK ²	X	X	X	X
Soluble Protein				X
Archived samples [serum; plasma]	X		X	
Optional Assessments				
Optional: fine needle aspiration of liver ³	X	X	X	X
Optional: PBMC Collection for immunophenotyping ³	X	X	X	X
Optional: Soluble Protein ⁴	X	X	X	X
Optional: PAXGene RNA for expression analysis in whole blood ⁴	X	X	X	X

1. Hematology- platelet count to be analyzed at local laboratory prior to dose; hematology samples to be collected for central laboratory assessments in parallel
2. PK samples are to be taken pre-dose.
3. An optional additional FNA may be collected anytime between Week 6 and Week 36 following discussion between investigator and medical monitor based on unexpected changes in HBsAg or ALT. Only 1 additional FNA may be collected for each participant.
4. Only to be collected if the optional FNA is collected at this visit and has not already been collected as part of the standard assessments.

Table 4 Off-Treatment Follow-Up Day 85 to Day 246

Assessments	Day 85	Day 92	Day 106	Day 134	Day 162	Day 190	Day 218	Day 246	Early Termination
Window	W 13	W 14	W 16	W 20	W 24	W 28	W 32	W 36	NA
Safety Assessments	± 3 days								
AE/SAE review	X	X	X	X	X	X	X	X	X
Concomitant medication review	X	X	X	X	X	X	X	X	X
Symptoms directed exam	X	X		X	X	X	X	X	X
Vital signs	X	X	X	X	X	X	X	X	X
Laboratory									
Pregnancy test (women of child bearing potential)	X		X	X	X	X	X	X	X
Hematology ¹ (includes platelet count, and WBC with differential)	X	X	X	X	X	X	X	X	X
PT, INR, aPTT	X	X	X	X	X	X	X	X	X
Chemistry	X	X	X	X	X	X	X	X	X
Urinalysis	X	X	X	X	X	X	X	X	X
Urine ACR	X	X	X	X	X	X	X	X	X
HBsAg and HBV DNA	X	X	X	X	X	X	X	X	X
Anti-HBsAg	X	X	X	X	X	X	X	X	X
Anti-HBeAg	X	X	X	X	X	X	X	X	X
HBV RNA, HBcAg, and Sequencing (HBV genotype/phenotype; HBV DNA and/or RNA)	X		X		X	X	X	X	X

Assessments	Day 85	Day 92	Day 106	Day 134	Day 162	Day 190	Day 218	Day 246	Early Termination
	W 13	W 14	W 16	W 20	W 24	W 28	W 32	W 36	NA
Complement C3, Complement C4, hs-CRP, MCP-1		X	X	X	X	X	X	X	X
Complement C5a, Complement factor Bb		X	X	X	X	X	X	X	X
ANCA, Ang II	X		X	X	X	X	X	X	X
PK	X	X	X	X	X	X	X	X	X
Fine Needle Aspiration of Liver ²	X							X	X
PBMC Collection for immunophenotyping								X	X
PAXGene RNA for expression analysis in whole blood	X				X			X	X
Soluble Protein	X		X		X		X	X	X
APRI/Fibrosure								X	X
Archived Samples [serum; plasma]	X	X	X	X	X	X	X	X	X
Optional Assessments									
Optional: fine needle aspiration of liver ³		X	X	X	X	X	X		
Optional: PBMC Collection for immunophenotyping ⁴		X	X	X	X	X	X		
Optional: Soluble Protein ⁴		X	X	X	X	X	X		
Optional: PAXGene RNA for expression analysis in whole blood ⁴		X	X	X	X	X	X		

1. Hematology- platelet count analyzed at local laboratory is **optional** during the off-treatment period; hematology samples to be collected for central laboratory assessments
2. FNA will only be collected if the investigator deems it appropriate
3. An optional additional FNA may be collected anytime between Week 6 and Week 36 following discussion between investigator and medical monitor based on unexpected changes in HBsAg or ALT. Only 1 additional FNA may be collected for each participant.
4. Only to be collected if the optional FNA is collected at this visit and has not already been collected as part of the standard assessments.

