10.2. Appendix 2: Clinical Laboratory Tests

The tests detailed in [Table 11](#) will be performed by the central laboratory. Local laboratory samples may still be collected as needed by the site.

Local laboratory results are required for analysis of platelets during the dosing period and be available for the investigator's review prior to dosing. A sample for central analysis is obtained in parallel

Otherwise, local laboratory results are only required in the event that the central laboratory results are not available in time for either study intervention administration and/or response evaluation. If a local sample is required, it is important that the sample for central analysis is obtained in parallel.

Protocol-specific requirements for inclusion or exclusion of participants are detailed in Section [5](#) of the protocol.

Additional tests may be performed at any time during the study as determined necessary by the investigator or required by local regulations.

Pregnancy Testing:

Refer to Section [5.1](#) Inclusion Criteria for screening pregnancy criteria. Additional serum or urine pregnancy tests may be performed, as determined necessary by the investigator or required by local regulation, to establish the absence of pregnancy at any time during the participant's participation in the study.

Table 11 Protocol-Required Laboratory Tests

Laboratory Assessments	Parameters			
Hematology	Platelet Count ¹	RBC Indices: MCV MCH	WBC count (with Differential if WBC abnormal): Neutrophils Lymphocytes Monocytes Eosinophils Basophils	
	RBC Count			
	Hemoglobin			
	Hematocrit			
Clinical Chemistry	Blood Urea Nitrogen (BUN)	Potassium	Aspartate Aminotransferase (AST)/ Serum Glutamic-Oxaloacetic Transaminase (SGOT)	Total, indirect and direct bilirubin
	Creatinine	Sodium	Alanine Aminotransferase (ALT)/ Serum Glutamic-Pyruvic Transaminase (SGPT)	Total Protein

Laboratory Assessments	Parameters			
	Glucose	Calcium	Alkaline phosphatase	Albumin
Routine Urinalysis	
 • By dipstick • Microscopic examination (if blood or protein is abnormal) 			
Pregnancy testing	
 • Highly sensitive urine or serum human chorionic gonadotropin (hCG) pregnancy test (as needed for women of childbearing potential)² 			

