#### **4.5.3. Additional Safety Assessments**

##### **4.5.3.1. Laboratory Data**

Only central lab data will be used for summary analyses and figures; local lab data will be included in listings, as appropriate.

Summary statistics for changes from baseline for each numeric parameter at each visit will be presented, separately for all clinical chemistry parameters, all hematology parameters and all urinalysis parameters.

For immunology parameters, summary statistics for actual value and change from baseline data for each parameter at each visit will be presented, separately for all numeric parameters. Listings will also be created.

For categorical immunology parameters c-ANCA and p-ANCA, summary table of baseline Negative to post-baseline Positive, baseline value no change, and baseline Positive to post-baseline Negative will be created. Listing will be created as well.

For coagulation parameters Prothrombin Intl. Normalized Ratio (INR), Prothrombin Time (PT) and Activated Partial Thromboplastin Time (aPTT), summary statistics for actual at each visit will be presented. Listing will be created as well.

Shift tables for laboratory parameters showing baseline toxicity versus maximum post-baseline (on-treatment and off-treatment periods combined) toxicity for each grade (Grade 1, Grade 2, etc.) for chemistry and hematology parameters will be provided.

Increase to Grade 3 or higher lab abnormalities for platelets, ALT, AST, INR, total bilirubin, serum creatinine, eGFR, ACR will be summarized.

Laboratory values outside of normal range will be summarized and listed.

Grading categories for laboratory tests are determined using the DAIDS grading system Version 2.1 [[National Institute of Allergy and Infectious Diseases. Division of AIDS, 2017](#)].

Summary of post-baseline hepatobiliary laboratory abnormalities will be provided based on both planned and unplanned assessments (e.g. unscheduled visit, monitoring event).

Liver monitoring and stopping event reporting will be summarized and listed. The Liver monitoring and stopping criteria are described in the protocol Section 7.1.1.

The worst-case urinalysis results post-baseline (on-treatment and off-treatment periods combined) relative to baseline will be summarized.

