#### 6.1.2. Demographic and Baseline Characteristics

Study population analyses including analyses of participant's disposition, protocol deviations, demographic and baseline characteristics, prior and concomitant medications, nucleos(t)ide treatment starting after randomization, medical history and exposure and treatment compliance will be presented.

Demographic characteristics including sex, age, ethnicity, race, height and weight will be summarized with descriptive statistics.

Baseline characteristics including hypertension, NSAID, TDF/TAF containing medications use, ADV containing medications use, diabetes, eGFR, serum creatinine, urine ACR, platelets, ANC, complement C3, complement C4, complement C5a, complement Bb, C Reactive Protein, MCP-1, c-ANCA, p-ANCA and subgroup categories listed in Section 4.6.1 will be summarized with descriptive statistics.

Hepatitis B characteristics, as collected on the Hep B Disease Characteristics eCRF, will be summarized using descriptive statistics, and will be listed.

A table and listing of nucleos(t)ide treatment at baseline will be presented.

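### The protocol gives three inconsistent rules for the white-cell differential, so a pre-dose differential is not assured, yet the SAP plans baseline ANC and change-from-baseline and shift tables for all haematology parameters

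*Protocol*

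**What the plan says.** **Protocol, what is collected**

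- Section 1.3, Table 1 (screening): "Hematology/Chemistry/Urinalysis", with no detail of content.
- Section 1.3, Table 2 (Week -1 to Day 50): "includes platelet count and WBC". A footnote to the row adds "hematology samples to be collected for central laboratory assessments in parallel".
- Section 1.3, Table 3 (Days 57 to 78): "includes platelet count and WBC with differential".
- Section 1.3, Table 4 (Days 85 to 246 and early termination): "includes platelet count, and WBC with differential".
- Appendix 2, Table 11, which sets out the central laboratory tests: "WBC count (with Differential if WBC abnormal", followed by neutrophils, lymphocytes, monocytes, eosinophils and basophils. The condition is not limited to particular visits.

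**SAP, what is to be analysed**

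- Section 4.5.3.1: "Summary statistics for changes from baseline for each numeric parameter at each visit will be presented", covering all haematology parameters. It adds shift tables of baseline grade against worst post-baseline grade for chemistry and haematology, and allows only central laboratory data into summaries.
- Section 6.1.2: the baseline characteristics include "platelets, ANC, complement C3".
- Section 4.1.2: baseline is the latest non-missing pre-dose value, unscheduled visits included. If there is none, baseline stays missing and nothing is derived.

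**The concern.** One test has three collection rules: not named, routine, and only when the total count is abnormal. Tables 3 and 4 conflict with Table 11 whatever Table 2 means, because a differential at every visit and a differential only on abnormal samples cannot both be the rule.

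The SAP depends on the outcome. Baseline ANC is named outright and needs a differential. The change-from-baseline and shift displays reach the five cell types because Table 11 lists them under haematology. If differentials are done only on abnormal counts, those displays describe a selected subset, and a cell type can be abnormal while the total count is normal.

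Timing adds some weight. Table 6 of the protocol expects ALT flares in responders to begin around Week 5, within the period of Table 2. The liver-event work-up asks sites to look for eosinophilia, and such a finding is easier to interpret against a routine pre-dose value.

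**Working it through.** No sample size, power or error rate is involved, and the plan states no figure to reproduce. The check is a visit count and a comparison of the passages.

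**Step 1. Count the scheduled haematology collections in Section 1.3.**

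| Table | Visits | Number | Differential named? |
|---|---|---|---|
| 1 | Screening | 1 | No detail |
| 2 | Week -1, Day 1 | 2 | No |
| 2 | Days 8, 15, 22, 29, 36, 43, 50 | 7 | No |
| 3 | Days 57, 64, 71, 78 | 4 | Yes |
| 4 | Days 85, 92, 106, 134, 162, 190, 218, 246 | 8 | Yes (also early termination) |

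After screening, 2 + 7 = 9 collections do not name the differential and 4 + 8 = 12 do. Before dosing there are 1 + 2 = 3 scheduled collections, and none names it. Day 1 counts as pre-dose because Table 2 places dosing after the assessments and SAP 4.1.2 treats untimed Day 1 values as pre-dose.

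**Step 2. Take each reading of the text and ask whether a pre-dose differential is assured.**

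| Reading | Screening to Day 50 | Day 57 onward | Pre-dose differential assured? |
|---|---|---|---|
| Schedule rows are complete lists | None in Table 2; screening unstated | Routine | No |
| Table 11 applies where the schedule is silent | Only if WBC abnormal | Routine | No |
| Table 11 applies throughout | Only if WBC abnormal | Only if WBC abnormal | No |
| A routine differential was meant at every visit | Routine | Routine | Yes, but no passage says so for pre-dose visits |

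**Step 3. Carry the second and third readings into the SAP.** A participant then has a baseline differential only if WBC was abnormal on at least one of the three scheduled pre-dose samples, or on an unscheduled one. It follows that:

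- baseline ANC summarises that subset, not the enrolled group;
- change from baseline is computed in the same subset, and because its members were chosen for an abnormal starting count, part of any movement towards normal would be regression to the mean;
- a participant with a normal pre-dose WBC has no baseline grade for the shift tables, even with a full set of differentials from Day 57 under the second reading;
- because the latest non-missing value is used, a participant with an abnormal WBC at screening and a normal one on Day 1 would have a baseline differential from an earlier date than the baseline WBC;
- a differential from a local laboratory cannot fill the gap in the summaries, since only central data enter them.

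The documents do not say how often a pre-dose WBC will be abnormal. With the planned 20 participants, the number with a baseline differential could lie anywhere from 0 to 20.

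**The case against.** The strongest reply is that the row labels are shorthand. The word used in Table 2 signals an incomplete list: the same label omits haemoglobin, haematocrit and red-cell count, which Table 11 requires and nobody would suppose were left out. Central samples are drawn at Week -1 and Day 1, a screening value can serve as baseline under SAP 4.1.2, and the planned baseline ANC suggests that the sponsor expects a neutrophil count.

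Most of this stands. A reader might infer from the schedule that no baseline differential exists at all, or that abnormalities can appear only from Week 9. The documents do not support either inference. Not naming a test in a label is not the same as not doing it, screening content is left open, and the Table 11 condition has no visit limit, so an abnormal WBC before Day 57 would trigger a differential.

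The reply does not secure the baseline, however. If the labels are shorthand, the detail must come from Table 11, and Table 11 makes the differential conditional. Screening values fall under the same condition. The baseline ANC entry shows intent, which is a reason to correct the collection rule.

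Two further points limit the consequence. SAP 4.5.3.1 names no neutrophil, lymphocyte or eosinophil table: these follow only from its reference to all haematology parameters, and it does not say which cell types are graded. Its list of Grade 3 or higher abnormalities contains no white-cell parameter. The mechanistic question rests on liver aspirates, PBMC immunophenotyping and whole-blood RNA, each scheduled at baseline and Day 29, not on the routine differential.

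**Conclusion.** The point holds as an inconsistency between passages that leaves a planned analysis without assured data. A pre-dose differential is not guaranteed for participants with a normal pre-dose WBC, and under Table 11 the baseline values available would come from a group selected for abnormal counts. It is not established that baselines will be absent, because laboratory practice may supply them.

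The size is modest. What is affected is baseline ANC and the haematology change-from-baseline and shift displays as they apply to white-cell types, all of them descriptive safety outputs. The primary endpoint, the sample size and platelet monitoring are untouched.

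The conclusion assumes that the SAP's reference to all haematology parameters includes the five cell types that Table 11 lists under that heading. For ANC at baseline no such assumption is needed.

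**What to change.** State one rule for the differential and use it in Section 1.3 Tables 1 to 4 and in Appendix 2 Table 11: a differential on every central haematology sample, including screening, Week -1 and Day 1. The samples are already drawn, so no extra visit is needed. The cost is a wording change in the protocol and laboratory manual and a small additional central-laboratory fee.

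If the conditional rule is kept, amend Tables 3 and 4 to match it and limit the ANC and differential displays in SAP 4.5.3.1 and 6.1.2 to what is collected. Report the number of participants with a baseline value beside each summary, and state that these values come from samples with an abnormal WBC. This costs only SAP text and table footnotes, but gives up a baseline that represents the whole group.
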